5.4 Interim analyses

There'll be no interim analysis for the study.

5.5 Subgroup analyses

There'll be no subgroup analysis for the study.

5.6 Sensitivity analyses

Different approaches for individual item missingness in OSS will be compared. Single imputation where missing items for a participant's OSS are substituted by the mean of their provided OSS items will be conducted. Furthermore, multiple imputation will be applied to individual items missing in the 12-item OSS questionnaire, assuming missing at random.

This will be done at each time point respectively for sets of results where there are no more than 2 items missing², as well as sets of results where there is at least 1 item completed.

Summary statistics derived will be presented together with summary statistics derived under complete case analyses for comparison (see table 13).

5.7 Information for CONSORT flow diagram

Flow of patients through study will be summarised in a CONSORT diagram, see Appendix 1.

6. Other analyses, data summaries, and graphs

6.1 Exploratory OSS analysis – Area Under Curve Summary Statistics

Inconclusive evidence suggested resolution of frozen shoulder symptoms within 12-24 months regardless of intervention for most patients. However, quicker resolution is preferable. The trajectory of OSS scores over time between treatment groups will therefore be explored using graphical summaries. Difference between groups over the whole follow-up period (rather than at single, fixed time points) will be assessed using area under the curve (AUC) summary statistics based on a linear combination of parameter estimates from the repeated measures mixed model formulated in 5.3.1 (see ref for details on parameter combination). Group specific estimates of AUC are calculated to inform the sample size calculation of the full trial should AUC be chosen as the primary outcome.¹²

6.2 Estimand framework

Inference on the proposed primary outcome for the full trial (OSS score) is complicated by the potential occurrence of inter-current events. Here we describe components of the estimand, inter-current events (IEs) identified *a priori* and strategies which theoretically could be used to handle them¹³.

Additional IEs observed will be added in the statistical analysis report. Strategies and implications for handling different IEs will be discussed with the clinical team at the analysis stage and a strategy for each IE will be selected based on suitability and viability.

The primary outcome estimand framework including its relevant sensitivity analysis strategies will be fully specified in the report. Sample size calculation suitable for the primary outcome estimand framework will also be specified in report. Frequencies of IEs (pre-specified + observed) will be tabulated by treatment arms.

Aspect	Definition
Target population:	
Participants who fulfil the following inclusion criteria:
 
 • Adults with frozen shoulder • Aged 18 years and older • Loss of passive external rotation of at least 50% compared with the contralateral side • Plain radiographs demonstrating the absence of glenohumeral osteoarthritis or other pathology 
And who do not meet the following exclusion criteria:
 
 • Recurrent ipsilateral frozen shoulder • Presentation following breast cancer or local radiotherapy • Known Rotator cuff tear • Long term systemic corticosteroid use or previous ipsilateral shoulder injection within 12 months
Variable/endpoint:	Oxford Shoulder Score (OSS)
Treatment conditions:	
Usual care group
 
Corticosteroid injection (CSI): with the patient in a lateral decubitus position and via a posterior approach, using an aseptic technique a needle will be inserted into the glenohumeral joint under ultrasound guidance. 3ml of 1% lignocaine, 3ml 0.25% bupivacaine and 80mg depomedrone will be infiltrated into the joint.

	
Intervention Group
 
Corticosteroid injection with hydrodilatation (CSI & HD): with the patient in a lateral decubitus position and via a posterior approach, using an aseptic technique a needle will be inserted into the glenohumeral joint under ultrasound guidance. 10ml of 1% lignocaine, 5ml 0.25% bupivacaine 80mg depomedrone and between 5 and 20ml of sterile normal saline will be injected into the glenohumeral joint under ultrasound guidance visualising the posterior capsule. The volume of fluid will be used to create capsular distention. Once capsular collapse/decompression occurs, injection of saline ceases. Injection of saline also ceases if the procedure is poorly tolerated. The total volume of injection is recorded. A minimum total of 20ml of fluid will be used to confirm a hydrodilatation has taken place.

Population level summary measure	Mean difference in change from baseline between groups
Intercurrent events	Suitable Strategies
Unforeseen un-associated shoulder/arm injury	While on treatment, hypothetical, treatment policy, principal stratum
Unrelated Serious Illness	While on treatment, hypothetical, treatment policy, principal stratum
Death	While alive, composite, principal stratum
Receiving surgery for injury	Treatment policy, while on treatment, composite, hypothetical, principal stratum
Receiving less than 20ml of fluid (CSI+HD arm only)	Treatment policy, hypothetical, principal stratum
Use of any non-study treatment in the follow-up period	Treatment policy, hypothetical, principal stratum
Receiving wrong dose of intervention	Treatment policy, hypothetical, principal stratum
Receiving the wrong intervention	Hypothetical, principal stratum

6.3 Safety analyses

SAE: We will report the total number of serious adverse events (SAEs) related to the ACCorD intervention overall and in each treatment group. We will also report the number of patients with at least one SAE by treatment group at injection visit (visit 2) and at each time point post injection (visit 3, visit 4, and visit 5).

AE: We will report the number of unexpected and expected AEs (complications) in each treatment group. We will also report the number of patients with at least one AE by treatment group at injection visit (visit 2) and at each time point post injection (visit 3, visit 4, and visit 5).

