Table 14 Adjusted treatment effects on OSS, EQ-5D-3L summary index, and ROM at post-randomisation time points if full trial is deemed infeasible.

	V3 (N=)	V4 (N=)	V5 (N=)
OSS			
Treatment - n/N (%)			
Control – n/N(%)			
Adjusted difference in mean OSS between treatment groups* - 95% confidence interval (CI)			
p-value			
EQ-5D-3L Summary Index			
Treatment - n/N (%)			
Control – n/N (%)			
Adjusted difference in mean EQ-5D-3L summary index between treatment groups* - 95% confidence interval (CI)			
p-value			
ROM			
Treatment - n/N (%)			
Control – n/N (%)			
Adjusted difference in mean ROM between treatment groups* - 95% confidence interval (CI)			
p-value			

*Direction of difference: treatment group mean – control group mean. Difference is adjusted for fixed effects (site, age, gender, baseline OSS) and interaction effects between baseline measurements and visits.

Table 15: Total number of AEs by treatment groups and overall

	Intervention (N=)	Control (N=)	Overall (N=)
Overall			
Complications/Expected AE			
Pain at injection site			
Cutaneous infection at injection site			
Loss of subcutaneous fat at injection site causing a skin dimple.			
Steroid flare (transient significant increase of pain symptoms lasting usually no more than 72 hours)			
Disturbance of menstrual cycle			
Transient weakness in arm muscles caused by local anaesthetic leaking around nerves and having a temporary numbing effect lasting no more than a couple of hours			
Significant disturbance in blood sugar level in diabetic patients due to administration of corticosteroid			
Development of septic arthritis due to the introduction of infection to the shoulder joint following injection			
Unexpected AE			

Table 16: Number and proportion of patients with at least 1 AE overall and in each treatment group by study visits

	Intervention (N=)	Control (N=)	Overall (N=)
Overall			
Injection visit			
V3			
V4			
V5			

Table 17: Total number of SAEs by treatment groups and overall

	Intervention (N=)	Control (N=)	Overall (N=)
Overall			
Death			
Life-threatening			
Requires in patient hospitalisation or prolongation of hospitalisation			
Results in significant disability or incapacity			
Congenital anomaly or birth defect			
Requires intervention to prevent permanent impairment			
Deemed by the PI to be medically significant			
Other important medical event			

Table 18: Number and proportion of patients with at least 1 SAE overall and in each treatment group by study visits

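### SAP 6.3 limits the SAE event total to intervention-related events, but its next sentence and dummy Tables 17 and 18 carry no such limit

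*SAP*

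**What the plan says.** Section 6.3 of the SAP defines the SAE event count first: "We will report the total number of serious adverse events (SAEs) related to the ACCorD intervention overall and in each treatment group". It then defines a patient count: "We will also report the number of patients with at least one SAE by treatment group at injection visit (visit 2"), and again at each later visit. The second sentence does not repeat the relatedness condition.

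Two dummy tables in Appendix 3 correspond to these sentences:

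- The event count has "Table 17: Total number of SAEs by treatment groups and overall". Below an overall row, its rows are seriousness criteria such as death, life-threatening events and hospitalisation. It has no row, column or footnote on relatedness.
- The patient count has "Table 18: Number and proportion of patients with at least 1 SAE overall and in each treatment group by study visits". It also has no relatedness condition.

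The parallel paragraph on adverse events reads "We will report the number of unexpected and expected AEs (complications) in each treatment group". It splits events by expectedness and does not filter them by cause.

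Section 6.2 lists "Unrelated Serious Illness" and death among the pre-specified intercurrent events, and adds that "Frequencies of IEs (pre-specified + observed) will be tabulated by treatment arms".

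**The concern.** The text and the table describe two different sets of events for the same number. Section 6.3 describes SAEs related to the intervention, and the title and rows of Table 17 describe SAEs in general. The SAP does not say which takes precedence, so two analysts could each follow the plan in good faith and publish different SAE totals.

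If the text is followed, unrelated serious events are missing from the total and from the seriousness breakdown. If the next sentence of 6.3 is read as it stands, the event count and the patient count then rest on different definitions, and the two tables need not agree with each other. The published SAE summary of a randomised study should be complete by arm and consistent within itself. This one could be neither.

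**Working it through.** The SAP gives no figure to reproduce here, so the check sets its statements side by side.

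| Place in the SAP | Quantity | Relatedness condition |
|---|---|---|
| 6.3, first SAE sentence | Number of SAEs | Yes, intervention-related only |
| 6.3, second SAE sentence | Patients with an SAE | None stated |
| Appendix 3, Table 17 | Number of SAEs | None in title or rows |
| Appendix 3, Table 18 | Patients with an SAE | None in title or rows |
| 6.3, AE paragraph | Number of AEs | None; split by expectedness |

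**Step 1: do the text and Table 17 agree?** No. They describe the same quantity, and only the text restricts it. The table rows do not resolve this, because seriousness criteria apply to any SAE, related or not.

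**Step 2: can the event and patient counts conflict?** For one arm, let R be the number of related SAEs, U the number of unrelated SAEs, and P the number of patients with at least one SAE of any kind.

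- Under one all-cause definition, the event total is R + U. Every patient counted in P has at least one event, so P ≤ R + U always holds.
- With the total restricted by the text and the patient count unrestricted, the event total is R alone, and P ≤ R need not hold.

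An illustration with assumed counts, which is not a forecast: three patients in an arm each have one unrelated SAE, and there are no related SAEs. Then R = 0, U = 3 and P = 3. Table 17 filled by the text shows 0. Filled by its title it shows R + U = 0 + 3 = 3. Table 18 read as titled shows 3 patients in both cases.

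**Step 3: is U expected to be zero?** The SAP does not suggest so. Section 6.2 names unrelated serious illness and death as intercurrent events to plan for. No expected number of SAEs is given, so the size of U cannot be estimated from this document.

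**Step 4: would the missing events appear elsewhere?** Some might, in the intercurrent-event frequencies by arm. That tabulation serves the estimand and is not defined by the SAE criteria, so it need not capture every unrelated SAE and does not replace an SAE count.

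**Step 5: is the restriction explained?** The SAP gives no reason for it. Read literally, the AE paragraph counts AEs without regard to cause while the SAE event total is filtered by cause.

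**The case against.** The best reply is that this is loose wording with limited consequences. Several parts of that reply stand.

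- **Omission is possible, not certain.** Nothing ranks 6.3 above the dummy tables. If Table 17 is filled as titled, no SAE is left out. The disagreement with the text would remain.
- **A single scope may be intended.** The abbreviation is introduced inside the restricted phrase, so the second sentence and the table titles could be shorthand for related SAEs. The two tables would then agree. This is a tenable reading, but the SAP does not state it, and on it unrelated serious events would appear in neither table.
- **The protocol may settle it.** Which SAEs are recorded is normally a protocol matter, and the protocol was not available for this review. If only related SAEs are recorded, the counts coincide.

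Two stronger readings are tempting, and the SAP does not support either as a finding.

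- **That the restriction hides an imbalance between arms.** If Table 18 is all-cause, as titled, it still shows patients with an SAE by arm, so a patient-level imbalance would be visible. What would be lost is repeat unrelated events within a patient and the breakdown by seriousness criterion. An imbalance could go unseen only if both tables were restricted.
- **That unblinded practitioners would bias the attribution.** Section 4.3 says those giving the injection cannot be blinded and that the assessor at 6 weeks is. The SAP does not say who assesses relatedness. A count that depends on that judgement is more exposed than an all-cause count, but this is a conditional risk and not a demonstrated fault.

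**Conclusion.** The point holds as an internal inconsistency of minor severity. Section 6.3 restricts the SAE event total to intervention-related events. Its next sentence and Tables 17 and 18 state no such restriction. Either Table 17 follows the text, and can leave out unrelated events and fall below the patient count in Table 18, or it follows its title and contradicts the text.

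The effect is confined to the SAE summary. Sample size, feasibility outcomes and the analyses of OSS, ROM and EQ-5D are not affected. The number of events involved cannot be given, because the SAP states neither an expected SAE count nor the share likely to be related.

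The conclusion about the two tables rests on reading the second sentence of 6.3 and the table titles as they stand, without an implied restriction. If a restriction was meant throughout, the tables are consistent with each other but their titles are incomplete.

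**What to change.** Reword the first SAE sentence of 6.3 so that it reports the total number of SAEs irrespective of relationship, overall and by treatment group. The text then matches Tables 17 and 18 as titled. Add a sub-row to Table 17 for SAEs related to the study injection, so that the related count is kept. The new wording should make clear that this means either study injection: the present term could be read as the hydrodilatation arm alone, although reporting it in each group suggests otherwise.

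The cost is one reworded sentence and one table row. No new data are needed provided the protocol records all SAEs. If it records only related SAEs, keep the restriction, but state it in both SAE sentences of 6.3 and in the titles of Tables 17 and 18, so that a reader does not take the counts as all-cause.

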6.4 Graphs

We will create a plot tracking the changes in treatment effect (mean OSS difference) and its 95% CIs throughout study.

We will create a Bland-Altman, regression-based, difference-vs-mean plot assessing the agreement between self-measured and clinician-measured ROM.

6.5 Withdrawal and deviations

Withdrawal: We will report the total number of withdrawals and the reasons for withdrawal overall and by treatment group at each time point. Reasons for withdrawal are specified in table 19 and categorised as follows:

- Withdrawal by PI
- Adverse event related
- Withdrawal by patient
 - Withdrawal by patient for intervention only
 - Withdrawal by patient for the whole study

Protocol deviation: We will report the total number of deviations and the types of deviations overall and by treatment group and site. The types of deviations are specified in table 21 and categorised as follows:

- Data deviation
- Deviation in consent
- Randomisation deviation
- Intervention deviation
- Follow-up deviation
- Others

6.6 Sample Size Calculation for Full Trial

From the observed paired OSS differences in this feasibility trial we obtain SD estimates, which we will use to calculate the sample size needed for a full trial, given power and significance level. The SD estimates will be used conservatively due to upwards bias of SD estimates from small samples.

Based on the final primary estimand specification (6.2) retention and data availability will be estimated and used for the sample size specification.

[figure not shown]
Recruitment rates observed in this feasibility trial would also be used to estimate the length of recruitment period needed for the full trial, given the number of sites and the overall required sample size.

7. References

1. Dawson, J., R. Fitzpatrick, and A. Carr. 'Questionnaire on the Perceptions of Patients about Shoulder Surgery'. *The Journal of Bone and Joint Surgery. British Volume* 78-B, no. 4 (July 1996): 593–600. <https://doi.org/10.1302/0301-620X.78B4.0780593>
2. Rangan, Amar, Stephen D Brealey, Ada Keding, Belen Corbacho, Matthew Northgraves, Lucksy Kottam, Lorna Goodchild, et al. "Management of Adults with Primary Frozen Shoulder in Secondary Care (UK FROST): A Multicentre, Pragmatic, Three-Arm, Superiority Randomised Clinical Trial." *The Lancet* 396, no. 10256 (October 2020): 977–89. [https://doi.org/10.1016/S0140-6736\(20\)31965-6](https://doi.org/10.1016/S0140-6736(20)31965-6)
3. Dawson, Jill, Katherine Rogers, Ray Fitzpatrick, and Andrew Carr. 'The Oxford Shoulder Score Revisited'. *Archives of Orthopaedic and Trauma Surgery* 129, no. 1 (January 2009): 119–23. <https://doi.org/10.1007/s00402-007-0549-7>
4. 'EuroQol - a New Facility for the Measurement of Health-Related Quality of Life'. *Health Policy* 16, no. 3 (December 1990): 199–208. [https://doi.org/10.1016/0168-8510\(90\)90421-9](https://doi.org/10.1016/0168-8510(90)90421-9)
5. Hernández Alava, Mónica, Steve Pudney, and Allan Wailoo. 'Estimating the Relationship Between EQ-5D-5L and EQ-5D-3L: Results from a UK Population Study'. *Pharmacoeconomics* 41, no. 2 (February 2023): 199–207. <https://doi.org/10.1007/s40273-022-01218-7>
6. Teare, M Dawn, Munyaradzi Dimairo, Neil Shephard, Alex Hayman, Amy Whitehead, and Stephen J Walters. 'Sample Size Requirements to Estimate Key Design Parameters from External Pilot Randomised Controlled Trials: A Simulation Study'. *Trials* 15, no. 1 (December 2014): 264. <https://doi.org/10.1186/1745-6215-15-264>

Appendix 1: Flow-diagram

Appendix 2: Derivation of all outcome measures

1. Feasibility outcome – recruitment

Proportion of eligible participants clinicians willing to recruit:

- No. of eligible participants clinicians willing to recruit/ no. of eligible participants presented to MSK hubs

Eligible participants clinicians are willing to recruit may refused to be recruited before randomisation. Therefore, to compute the no. of eligible participants clinicians are willing to recruit, we add the total number of participants clinicians recruited (total number of participants eventually randomised) and the total number of eligible participants who refused to be recruited.

2. Oxford Shoulder Score (OSS)

The OSS is a validated patient self-reported instrument developed with patients, including those with frozen shoulder¹; it has been used in randomised trials of patients with frozen shoulder and in long-term follow-up studies.²

The OSS is a 12-item measure. Each of the 12 items has 5 potential answers and is scored from 4 (best/fewest symptoms) to 0 (worst/most severe). The total score is the sum of the 12 individual items and therefore ranges from 0 to 48; lower score indicates greater degree of disability.^{1,3}

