3.1 Feasibility outcomes

The feasibility outcomes measured are:

Recruitment

- The average rate of eligible participants presenting to MSK hubs per month:
 - o No. of eligible participants presenting to MSK hubs during recruitment period/ length of recruitment period (in months)
- Proportion of eligible participants clinicians willing to recruit (see appendix 2 for more detail):
 - o No. of eligible participants clinicians willing to recruit/ no. of eligible participants presented to MSK hubs
- Proportion of eligible participants that are randomised:
 - o No. of eligible participants randomised/ no. of eligible participants presented to clinicians.

Adherences

- Participant adherence to study protocol:
 - o No. of participants receiving injections / no. of randomised participants

Retention

- General retention:
 - o No. of participants who provided any follow-up data / no. of randomised participants for study visits listed in section 3.2, overall and by treatment groups
- Oxford Shoulder Score (OSS) questionnaire retention:
 - No. of participants who answered any OSS items / no. of randomised participants for study visits listed in section 3.2, overall and by treatment groups

Data completeness

- Proportion of missingness in each outcome at each time point (as specified in section 3.2), overall and by reasons of missingness (where available):
 - o No. of participants who provided complete outcome (usable in analysis without imputation)/ no. of randomised participants
- Proportion of randomised participants who returned resource use questionnaire, by study visits, overall and by reason of missingness (where available):
 - o No. of randomised participants who returned resource use questionnaire/ no. of randomised participants for study visits listed in section 3.2 where such a questionnaire is due
- Proportion of randomised participants who were successfully linked to administrative primary care records
 - o No. of randomised participants successfully linked to administrative primary care records/ no. of randomised participants
- Proportion of randomised participants who were successfully linked to administrative hospital care records
 - o No. of randomised participants successfully linked to administrative hospital care records/ no. of randomised participants

Concordance of health care data collected with case report forms against routinely collected linked data

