4.1 Sample size calculation

There is no agreed procedure for estimating appropriate sample sizes in feasibility studies. Guidelines suggest recruiting 50-70 participants.^{6,7} Correspondingly, we have selected a convenience sample of 66 participants to determine our ACCORD Protocol version 3.0, 18 November 2022 Page 23 of 32 feasibility objectives. The 95% confidence interval (CI) for a rate estimated to answer a feasibility objective would be at most +/-12.2% wide with a sample size of n=66.

We expect 10 people per month to be diagnosed with frozen shoulder in each MSK Hub. If 25% of these are ineligible and half of the remaining consent to participate in the study, we expect to be able to recruit 2-4 participants per month per site and therefore the convenience sample of 66 participants within 6 months. If these rates were confirmed, we would be able to recruit the required definitive trial sample (anticipated number including attrition=448) within approximately 14 months from 8 Hubs, based upon a recruitment rate of 4 per centre per month and an attrition estimate of 15%.

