4.2 Randomisation procedure

Randomisation will only occur when the research team confirms eligibility, and the participant has provided written, informed consent.

Participants will be randomised in a 1:1:1:1 ratio, stratified by recruiting centre, to one of the following:

- CSI&HD and patient to self-measure ROM self-measured before 6 week (+/- 3 days) visit
- CSI&HD and patient to self-measure ROM self-measured after 6 week (+/- 3 days) visit
- CSI alone and patient to self-measure ROM self-measured before 6 week (+/- 3 days) visit
- CSI alone and patient to self-measure ROM self-measured after 6 week (+/- 3 days) visit

The allocation will be determined just prior to the time of the injection, using a web-based, distant randomisation service administered by the Pragmatic Clinical Trials Unit, QMUL. Allocation lists using random permuted blocks of sizes 4 and 8 will be prepared by the trial statistician with the final lists being uploaded to the randomisation system by an independent statistician.

The clinician providing the injection will contact a member of the research team once the participant has arrived for their appointment. The research team member who is appropriately and sufficiently trained and delegated to complete randomisation will randomise the patient and communicate the allocation to the treating clinician.

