	Intervention (N=)	Control (N=)	Overall (N=)
Overall			
Injection visit			
V3			
V4			
V5			

Table 19: Reasons for withdrawal overall and by treatment group

	Intervention (N=)	Control (N=)	Overall (N=)
Overall			
Withdrawal by PI			
Adverse event related			
Withdrawal by patient			
Withdrawal by patient for intervention only (data will be collected up to date of withdrawal)			
Withdrawal by patient for whole study			

Table 20: Number and proportion of withdrawals overall and by treatment group at each time point

	Intervention (N=)	Control (N=)	Overall (N=)
Overall			
V1/Baseline			
V2/ Injection Visit			
V3			
V4			
V5			

Table 21: Number and types of deviations overall and by site

	Tower Hamlets	Newham	Waltham Forest	Cambridgeshire and Peterborough	Overall
Overall					
Data deviation					
Deviation in consent					
Randomisation deviation					
Intervention deviation					
Follow-up deviation					
Others					

Table 22: Number and types of deviations overall and by treatment groups

	Intervention	Control	Overall
Overall			
Data deviation			
Deviation in consent			
Randomisation deviation			
Intervention deviation			
Follow-up deviation			
Others			

Table 23: Participant experience questionnaire overall and by treatment groups

	Intervention (N=) – n/N (%)	Control (N=) – n/N (%)	Overall (N=) – n/N (%)
Participation Questionnaire			
The participant information sheet was easy to understand			
Strongly Agree			

Agree			
Neutral			
Disagree			
Strongly Disagree			
Missing			
Education information/booklet about managing frozen shoulder was easy to understand			
Strongly Agree			
Agree			
Neutral			
Disagree			
Strongly Disagree			
Missing			
Education about managing frozen shoulder was helpful in my recovery			
Strongly Agree			
Agree			
Neutral			
Disagree			
Strongly Disagree			
Missing			
The process of speaking with the research team about the study before I joined was helpful			
Strongly Agree			
Agree			
Neutral			
Disagree			
Strongly Disagree			
Missing			
The consent process was easy to understand and complete			
Strongly Agree			
Agree			
Neutral			
Disagree			
Strongly Disagree			
Missing			
I enjoyed participating in the study			
Strongly Agree			
Agree			
Neutral			
Disagree			

Strongly Disagree			
Missing			
I would participate in another research study in the future			
Strongly Agree			
Agree			
Neutral			
Disagree			
Strongly Disagree			
Missing			
Experience on attending study visits			
Visit1 - Baseline			
Face-to-face			
Phone			

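### The clinician-willingness numerator has no term for patients who consented but were not randomised for a reason other than refusal, so the proportion is understated

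*SAP*

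**What the plan says.** Section 2 of the SAP lists clinician willingness to recruit as a feasibility objective in its own right, separate from the proportion randomised. Sections 3.1 and 5.2.1 define it as a ratio: "No. of eligible participants clinicians willing to recruit/ no. of eligible participants presented to MSK hubs". Table 3 reports it by hub and overall.

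Appendix 2, item 1, says how the numerator is obtained. It first gives a reason: "Eligible participants clinicians are willing to recruit may refused to be recruited before randomisation". It then gives the rule: "we add the total number of participants clinicians recruited (total number of participants eventually randomised) and the total number of eligible participants who refused". The rule counts no clinician decision directly and treats recruited as meaning eventually randomised.

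Section 4.2 fixes the order of events. "Randomisation will only occur when the research team confirms eligibility, and the participant has provided written, informed consent". On timing: "The allocation will be determined just prior to the time of the injection". On the trigger: "The clinician providing the injection will contact a member of the research team once the participant has arrived for their appointment". The schedule in section 3.2 places baseline at Visit 1 and the intervention at Visit 2.

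**The concern.** The outcome is meant to show whether clinicians will put eligible patients forward. The rule infers this from what happened to the patient, and it recognises only two outcomes as evidence of a willing clinician: randomised, or refused. Because randomisation waits for the injection appointment, there is a gap between consent and randomisation. A patient can be lost in that gap without refusing, and the rule then subtracts that patient from clinician willingness.

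What is at stake is the interpretation of a named feasibility outcome. Clinician reluctance and loss between consent and injection are different obstacles to a definitive trial and call for different responses. The rule reports some of the second as the first. The adherence, retention and outcome-completeness measures in section 3.1 all have randomised participants as their denominator, so none of them would show the loss either.

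**Working it through.** **The plan's own figure.** The SAP states no expected value for clinician willingness, so there is none to reproduce. The planning funnel in section 4.1 starts from "We expect 10 people per month to be diagnosed with frozen shoulder in each MSK Hub". With 25% ineligible and half of the rest consenting, it gives 10 × 0.75 × 0.5 = 3.75 per hub per month, inside the stated 2 to 4.

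**Symbols**
- E: eligible patients presenting to the hubs (the denominator in section 3.1)
- R: patients randomised
- F: eligible patients who refused
- L: eligible patients whom the clinician agreed to recruit, who consented and did not refuse, and who were not randomised

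A patient found ineligible after consent would leave E as well, and is not counted in L.

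**Formulas**, taking the refusers as the SAP's reasoning presents them, that is, as patients of willing clinicians:
- Appendix 2 rule: (R + F)/E
- Quantity defined in section 3.1: (R + L + F)/E
- Rule minus definition: −L/E

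F cancels, so the size of the error does not depend on how many patients refuse. It is zero only if L = 0.

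**Inputs**
- R = 66, the planned sample (section 4.1).
- E = 66/0.5 = 132, from the section 4.1 planning rate that half of eligible patients consent, with randomised set equal to consented.
- F = 40, assumed, to give the proportions a level.
- L = 0, 5 or 13, assumed. As a share of consenters, 5/(66 + 5) = 7.0% and 13/(66 + 13) = 16.5%.

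| L | Appendix 2 rule | Section 3.1 definition | Error (points) |
|---|---|---|---|
| 0 | 106/132 = 80.3% | 106/132 = 80.3% | 0 |
| 5 | 106/132 = 80.3% | 111/132 = 84.1% | −3.8 |
| 13 | 106/132 = 80.3% | 119/132 = 90.2% | −9.8 |

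**Sensitivity to E.** If half of eligible patients consent and L of those consenters are lost, E is (66 + L)/0.5. That is 142 for L = 5 and 158 for L = 13, and the error becomes 5/142 = 3.5 and 13/158 = 8.2 points. The order of size is the same.

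**Does the SAP allow for such patients?** Table 20 has a row for withdrawals at V1/Baseline, ahead of the injection visit. Table 19 includes withdrawal categories other than the patient's own choice. Neither table feeds the Appendix 2 numerator.

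**The case against.** The strongest reply is that Appendix 2 speaks of refusing before randomisation and equates recruitment with randomisation. A patient who consents and then changes their mind before the injection can therefore be counted as a refuser, and is not lost from the numerator. This stands. It confines the problem to losses that are not refusals, and it means that consented-but-not-randomised patients as a whole cannot be assumed to be dropped.

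A second reply concerns consequence. The SAP sets no threshold for willingness and attaches no decision rule to it, and section 6.6 projects the recruitment period of the full trial from observed recruitment rates. This also stands. It cannot be said from this document that the decision on a definitive trial would change.

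A reader might go further and infer that the rule also errs upwards, by crediting every refuser with a willing clinician, so that the bias could run either way. The SAP does not support that as a finding. The sentence before the rule introduces the refusers as patients whom clinicians were willing to recruit. If patients are offered the study only after the clinician agrees, adding all refusers is correct. The experience questionnaire in Table 23 has the item "The process of speaking with the research team about the study before I joined was helpful", which shows that the research team discusses the study with patients but not whether the clinician has agreed by then. The approach pathway is a matter for the protocol, which was not available for this check. What remains is a looseness of wording: the reasoning presumes prior agreement, while the rule adds the total.

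**Conclusion.** The point holds in one direction. As written, the Appendix 2 rule understates clinician willingness by L/E whenever a patient whom the clinician agreed to recruit consents and is then not randomised for a reason other than refusal. The mechanism follows from Appendix 2 read with section 4.2 and needs no outside information.

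The size is not known. The illustration of about 4 to 10 points rests on assumed values of L (5 to 13) and on E = 132 from the planning rates. If no such losses occur, the error is nil. An overstatement through refusers is not shown, and neither is a wrong feasibility decision. This is a definition to correct before the outcome is reported.

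**What to change.** In Appendix 2, item 1, make three changes and carry them into Table 3:

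1. Add to the numerator the eligible patients who consented but were not randomised, counting each patient once so that a consenter who later refused is not entered twice. Show this count on its own line.
2. State that refusers are patients who declined after the clinician had agreed to offer them the study. This puts the SAP's own presumption into the rule.
3. Show eligible patients with no recorded clinician decision as unknown, neither willing nor unwilling.

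Taking all eligible patients and subtracting those with a recorded clinician reason for non-recruitment would be simpler. It is not advised, because it would count patients who were never approached as having a willing clinician and so introduce an upward error.

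The cost is a small re-derivation from the screening records. Where those records do not hold the clinician's decision, the unknown group will be larger and the proportion correspondingly less informative.
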